7.1.2 Temporary Discontinuation

Every attempt should be made to maintain participants on the study intervention during the course of the study. If the study intervention has been interrupted, it should be re-introduced as soon as, in the opinion of the investigator and the participant wishes to resume, the participant is able to re-start study treatment. The treatment period will not be extended to compensate for the temporary discontinuation. Note related to AESI skin reactions (including maculopapular rash): In the occurrence of maculopapular rash CTCAE Grade 1, 2, and 3, or generalised rash/skin reaction without an alternative suspect COPD medication (per Section 7.1.1), or serious rash/skin reaction, study intervention should be permanently discontinued.

At each visit, participants will be instructed to stop the study intervention and contact the investigator immediately if rash or skin reaction has developed. If, after the participant has

been seen by the study doctor or designee, the skin reaction does not meet permanent discontinuation criteria per Section 7.1, the study treatment can be restarted.

In the event that a participant develops symptoms suggestive of COVID-19 infection, the participant should undergo confirmatory rapid screening test for SARS-CoV-2 or PCR testing as soon as possible. Rapid screening test could be either lateral flow test/antigen test or molecular test. If the rapid screening test or PCR test confirms COVID-19 infection, the study intervention should be immediately discontinued on a temporary basis, unless any permanent discontinuation criteria are met (Section 7.1). After discontinuation of study intervention, any appropriate treatment is allowed if conditions presented in Section 6.9 are met.

In the event that a participant develops symptoms suggestive of pneumonia, the participant should undergo confirmatory chest x-ray and appropriate blood testing (eg, hsCRP, complete/full blood count, procalcitonin as deemed appropriate by the investigator) as soon as possible. If chest x-ray confirms the presence of consolidation and clinical markers are consistent with acute infection, the study intervention should be immediately discontinued on a temporary basis, unless any permanent discontinuation criteria are met (Section 7.1). After discontinuation of study intervention, any appropriate treatment is allowed if conditions presented in Section 6.9 are met.

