7.1.3 Restarting After Temporary Discontinuation

Participants who have temporarily discontinued study intervention can resume treatment as soon as, in the opinion of the investigator, the participant is able to re-start study treatment and the participant wishes to resume. No minimum time period is necessary before treatment can

resume, with the exception of participants who temporarily discontinued due to COVID-19, pneumonia or serious infection:

- If the study intervention has been temporarily discontinued due to confirmed COVID19 infection, it may be possible to resume the study intervention at least 7 days after the confirmatory rapid screening test or PCR test if, in the opinion of the investigator, the symptoms related to COVID19 were mild and have resolved.
- If the study intervention has been temporarily discontinued due to confirmed pneumonia or serious infection, it may be possible to resume the study intervention at least 7 days after completion of anti-microbial therapy if, in the opinion of the investigator, the symptoms related to pneumonia or serious infection were not severe and have resolved.

If the participant misses a scheduled visit during temporary discontinuation of study intervention, the missed visit should be recorded as "not done", unless:

- SV5 is missed, in which case it should be performed as soon as possible (eg, when the investigator believes an episode of serious infection, pneumonia or COVID19 has resolved).
- SV7 is missed, in which case it should be performed as soon as possible (eg, when the investigator believes an episode of serious infection, pneumonia or COVID-19 has resolved). The participant should not be re-dosed, but should complete all assessments as per the visit and continue in follow-up (this will ensure data are available at SV7 for the analysis).

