The study is powered using COPDCompEx, a composite endpoint used to estimate the magnitude of treatment effect on moderate and severe exacerbations of COPD. The time to first COPDCompEx event will be compared between AZD4831 QD vs placebo arms using a logrank test. A total of 194 first COPDCompEx events (estimated to require 203 participants per arm) will provide 80% power at the two-sided 10% level of statistical significance to detect a hazard ratio of 0.70 in the AZD4831 5 mg QD arm based on a 24-week first COPDCompEx event risk of 55% assumed in the placebo arm (constant over the course of the study). A screen failure rate of 40% is assumed, therefore approximately 677 participants will be screened to achieve the randomisation of 406 participants.

Cough Monitoring Substudy

A cough monitoring substudy will be performed alongside this study, where a subset of participants (maximum of 50 participants from each arm) from selected sites will be included. Twenty-four-hour cough frequency monitoring will be conducted at Visit SV3 (start of treatment) and Visit SV5 (after 12 weeks of treatment) using the VitaloJAK® Cough Monitor device. The main objective of the substudy is to explore the effect of AZD4831 compared with placebo on change in average 24-hour, awake, and sleeping cough frequency between baseline and Week 12. The substudy will also investigate whether average cough frequency is associated with lung function (e.g., PEF or FEV1), cough/COPD symptom scores (e.g., BCSS, CAT, and cough VAS) and sputum/blood biomarkers (e.g., MPO concentration).

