4.2.1 Primary Endpoint – Time to First COPDCompEx Event

4.2.1.1 Definition

The COPDCompEx is a composite endpoint developed to estimate the magnitude of treatment effect on COPD exacerbations over 52 weeks, in a 12-week study. It incorporates change in symptoms, reliever use and PEF obtained from daily diary, with confirmed exacerbations and/or study drop-outs.

The definition of the event is one of the following criteria:

- Moderate or severe exacerbations: episodes leading to one or more of the following: hospitalization, emergency room visit, an episode of pneumonia, treatment with OCS or corticosteroid depot injection, or treatment with antibiotics.
- *Diary events*: defined by threshold and slope criteria using the following diary and home spirometry variables: overall symptom rating, reliever medication use, and change in PEF.
- *Study dropouts*: early treatment discontinuation due to lack of efficacy.

The COPDCompEx definition and derivation are detailed in AZ Business Rules.

Time to first COPDCompEx event is defined as time elapsed from the start of study treatment to the occurrence of the first COPDCompEx event.

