4.2.1.3 Handling of Dropouts and Missing Data

The "while on treatment" strategy will be used for the primary estimand: if an intercurrent event occurs before first COPDCompEx event, the patient will be censored at the time of intercurrent event.

For participants who do not experience an on-treatment COPDCompEx event,

• If intercurrent event is earlier than date of last dose or the last eDiary date, the participant will be censored at intercurrent event date.

• If the intercurrent event is after the last eDiary date, but earlier than date of last dose, participants who do not experience an on-treatment COPDCompEx event, date of censoring will be last day of eDiary recording.

Intercurrent events are events occurring after treatment initiation (eg, premature treatment discontinuation, switching treatment, terminal events such as death) that affect either the measurement or interpretation of the summary measure (eg, hazard ratio) associated with the clinical question of interest. This study contains 2 intercurrent events:

- 1. Treatment discontinuation (with the following reasons: SAE, death not due to exacerbation, COVID-19, pneumonia, other).
- 2. Prohibited medication.

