4.2.2 Secondary Endpoint – Time to First Moderate or Severe COPD Exacerbation Event

4.2.2.1 Definition

A moderate or severe AECOPD may leads to any of the following:

- Use of systemic corticosteroids for at least 3 days; a single depot injectable dose of corticosteroids will be considered equivalent to a 3-day course of systemic corticosteroids.
- Use of antibiotics to treat COPD exacerbation for at least 3 days.
- An inpatient hospitalization due to COPD (defined as an inpatient admission ≥ 24 hours in the hospital, an observation area, the emergency department, or other equivalent healthcare facility depending on the country and healthcare system).
- Admission in emergency department or emergency room due to COPD for < 24 hours requiring intensive treatment.
- An episode of pneumonia.
- Results in death.

The start and stop of a moderate or severe exacerbation is defined as:

- The start date of systemic corticosteroids or antibiotic treatment or hospital/emergency admission, whichever occurs earlier, and the stop date is defined as the last day of systemic corticosteroids or antibiotic treatment or hospital/emergency discharge, whichever occurs later.
- A single depot injectable dose of corticosteroids will be considered equivalent to a 3-day course of systemic corticosteroids. The corresponding stop date for this treatment will consequently be determined as the date of administration plus 2 days.
- If multiple treatments are prescribed for the same exacerbation, the earliest start date and the latest stop date will be used.

For a severe COPD exacerbation with no documented corticosteroid or antibiotics treatment, hospitalization admission/discharge dates, or emergency visit date will be used as start/stop dates

A COPD exacerbation will be considered **moderate** if it requires treatment with systemic corticosteroids and/or antibiotics for at least 3 days or resulted in emergency room visit< 24 hours requiring intensive treatment; and does not result in hospitalization or death.

A COPD exacerbation will be considered **severe** if it results in hospitalization (defined as an inpatient admission \geq 24 hours in the hospital, an observation area, the emergency department, or other equivalent healthcare facility depending on the country and healthcare system) or death due to COPD.

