4.2.10 Tertiary/Exploratory Endpoint – Annualised rate of COPDCompEx Event

4.2.10.1 Definition

The COPDCompEx definition and derivation are detailed in AZ Business Rules.

Events regardless of what type (i.e., acute worsening or exacerbation) must be separated by at least 14 days in order to count as separate events (i.e., there must be at least 14 days during which no criteria for events are fulfilled).

The time during the event and the 14 days after each event will not be considered when defining time at risk for the COPDCompEx event rate. Time at risk (days) will be defined as

[Date of last dose of study intervention – date of the first dose of study intervention] + 2 – recovery time.

Where recovery time is defined as:

$$\sum_{i=1}^{k} [min(i^{th} event end date + 14, date of last dose of study intervention) - i^{th} event start date + 1]$$

4.2.10.2 **Derivations**

Annualised rate of COPDCompEx events, based on the period from baseline to last dose, will be calculated as:

Annualised rate of COPDCompEx events

Total number of COPDCompEx events

Total number of COPDCompEx events

(Date of last dose of IP – Date of the first dose of IP – recovery time + 2)/365.25

For participants who do not experience an on-treatment COPDCompEx event, date of censoring will be the last dose date or last date of eDiary recording whichever is earlier.

For CompEx analyses, only on-treatment events (i.e., events occurring from randomisation up to and including the last dose day) will be considered.

4.2.10.3 **Handling of Dropouts**

The "while on treatment" strategy, same as defined in section 4.2.1.3.

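### A pneumonia that ends treatment can be censored by its own consequence: it is both a primary event and a censoring reason, and no rule says which prevails

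*SAP*

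**What the plan says.** - **Pneumonia is an event.** SAP 4.2.1.1 defines the exacerbation component of COPDCompEx as an episode leading to "hospitalization, emergency room visit, an episode of pneumonia, treatment with OCS or corticosteroid depot injection, or treatment with antibiotics". SAP 4.2.2.1 and Protocol 8.2.2.1 also list pneumonia among the criteria for a moderate or severe exacerbation.
- **Stopping for pneumonia is a censoring reason.** SAP 4.2.1.3 gives as the first intercurrent event "Treatment discontinuation (with the following reasons: SAE, death not due to exacerbation, COVID-19, pneumonia, other". A participant whose intercurrent event precedes the first COPDCompEx event is censored at that point. SAP 4.2.2.3 applies the same rule to time to first exacerbation.
- **The window has no lag.** SAP 3.3.2 ends the on-treatment period at the last dose. SAP 4.2.10, under Derivations, says that for CompEx analyses "only on-treatment events (i.e., events occurring from randomisation up to and including the last dose day) will be considered". SAP 4.2.1.2 censors participants without an on-treatment event at the last dose or last eDiary date, whichever is earlier.
- **The event is dated by treatment or admission.** SAP 4.2.2.1 sets the start at "The start date of systemic corticosteroids or antibiotic treatment or hospital/emergency admission, whichever occurs earlier". Symptom onset and X-ray date play no part.
- **Drug is interrupted at confirmed pneumonia.** Protocol 7.1.2: "If chest x-ray confirms the presence of consolidation and clinical markers are consistent with acute infection, the study intervention should be immediately discontinued". By default this stop is temporary; it is permanent only where a criterion for permanent discontinuation applies. Protocol 7.1.3 allows resumption if, among other conditions, "the symptoms related to pneumonia or serious infection were not severe and have resolved". After 28 or more continuous days off drug, withdrawal from study drug is permanent (Protocol 7.1.2).

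**The concern.** When the pneumonia and the discontinuation come from the same episode, only the order of two dates decides whether the participant is an event or is censored. A tablet missed while ill, or an antibiotic started the day after the last tablet, is enough to reverse the outcome. The intercurrent-event list already accepts that an endpoint event should not censor itself, because it excludes deaths due to exacerbation. Pneumonia, SAE and the residual category carry no such exclusion.

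The protocol version history suggests how this arose: version 3.0 added the list with pneumonia in it, and version 4.0 later moved pneumonia into the exacerbation definition.

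Censoring that is caused by the event is informative. Impaired host defence with infection, including pneumonia, is a named potential risk of this drug (Protocol Table 2). If active treatment raises pneumonia, the lost events fall mostly in the active arm and the hazard ratio moves in its favour. Time to first exacerbation is more exposed than the primary endpoint: it has no diary events, so the same pneumonias are a larger share of its events.

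**Working it through.** **The plan's own figure first.** SAP 3.3 states "A total of 194 first COPDCompEx events (estimated to require 203 participants per arm") and that these "will provide 80% power at the two-sided 10% level of statistical significance to detect a hazard ratio of 0.70". Schoenfeld: 4 × (1.645 + 0.842)² / (ln 0.70)² = 194.4, which agrees with 194. Power at 194 events: Φ(√(194/4) × 0.3567 − 1.645) = 79.9%. With 55% risk on placebo, active risk is 1 − 0.45^0.70 = 42.8%. The mean is 48.9%, so 194 / 0.489 / 2 = 198 per arm, close to the 203 stated. This point does not disturb those figures.

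**Applying the date rules.** The study days are examples. Dosing is each morning (Protocol 6.2), and the dating follows SAP 4.2.2.1.

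| Case | Course | Last dose | Start date | Result |
|---|---|---|---|---|
| A | Dose taken, admitted same day, never restarts | 40 | 40 | Event, day 40 |
| B | Ill, day-40 dose not taken, admitted day 40, never restarts | 39 | 40 | Censored, day 39 |
| C | Confirmed after the day-40 dose, antibiotic next day, never restarts | 40 | 41 | Censored, day 40 |
| D | As C, but restarts and completes; interruption not an intercurrent event | 168 | 41 | Event, day 41 |
| E | As D, but interruption read as an intercurrent event | 168 | 41 | Censored, day 40 |

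A and B differ by one tablet. C and D differ only in restarting. D and E differ only in how the intercurrent event is read, and the SAP does not settle that: 4.2.1.3 speaks of treatment discontinuation, while the Table 9 footnote adds the qualifier premature.

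**Power.** The documents give no pneumonia rate, so the losses are assumed. With d events, power is Φ(√(d/4) × 0.3567 − 1.645).

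| Events lost | d | Power |
|---|---|---|
| 0 | 194 | 79.9% |
| 2 | 192 | 79.6% |
| 6 | 188 | 78.8% |
| 10 | 184 | 78.1% |
| 20 | 174 | 76.0% |

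**Bias.** Let shares p (placebo) and a (active) of first events be censored in this way. The apparent hazard ratio is then the true one × (1 − a)/(1 − p). The last column uses 203 per arm followed for 24 weeks at the planned placebo risk.

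| p / a (assumed) | True 1.00 appears as | True 0.70 appears as | False result favouring active |
|---|---|---|---|
| 2% / 2% | 1.000 | 0.700 | 5.0% |
| 1% / 3% | 0.980 | 0.686 | 6.8% |
| 2% / 5% | 0.969 | 0.679 | 7.8% |
| 3% / 10% | 0.928 | 0.649 | 13.6% |

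Example, third row: 0.95/0.98 = 0.969. Expected events are 203 × [(1 − 0.45^0.98) + (1 − 0.45^0.95)] = 218. Then √(218/4) × (−ln 0.969) = 0.23, and Φ(0.23 − 1.645) = 7.8%.

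**The case against.** The strongest reply is that few participants can be caught. The interruption is temporary by default. A dose taken on the start day keeps the event, and an earlier diary event means the participant is already counted. The supportive treatment-policy analysis (SAP 4.2.1.6) counts events after an intercurrent event. The COPDCompEx derivation sits in business rules outside the documents, which the version history says were revised for pneumonia and which may date it differently. Protocol Table 2 calls the infection risk theoretical and reports no increase so far. Ending the window at the last dose may also be a deliberate choice.

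Most of this stands and limits the size. It does not supply a precedence rule. The treatment-policy analysis is supportive only and uses data up to the end-of-treatment visit (SAP 4.2). SAP 4.2.1.5 plans no sensitivity analysis of the primary endpoint. Time to first exacerbation has neither a sensitivity nor a supplementary analysis (SAP 4.2.2.5, 4.2.2.6).

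Two stronger readings are tempting, and the documents do not support them:

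- A reader might infer that the protocol's stop itself pushes the event off treatment. The stop follows confirmation by X-ray and clinical markers. If treatment or admission falls on the day of the last tablet, the event counts. The gap needs a missed tablet, or treatment that starts on a later day.
- A reader might infer that the worst pneumonias are systematically lost. Severe cases are less likely to restart, but admission itself dates a hospitalised case. Loss requires both non-restart and a last dose before the start date.

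**Conclusion.** The gap is real but narrow. One pneumonia can be both the event and the cause of the discontinuation, and the plan leaves the outcome to a one-day difference in dates. The same applies to another qualifying episode that ends treatment under the SAE or residual reasons.

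The number of cases cannot be known from the documents and is probably small. The power loss is small: under two percentage points for 10 lost events. If pneumonia is equally frequent in both arms, the hazard ratio does not move. If it is more frequent on active, the bias favours active: an apparent 0.980 to 0.928 for a true 1.00 across the unequal shares shown, all of which are assumptions. The conclusion also assumes that the business rules date pneumonia as SAP 4.2.2.1 does. It should be settled before unblinding; it is no reason to change the event target or sample size.

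**What to change.** Add to SAP 4.2.1.3 and 4.2.2.3, and apply in 4.2.10 and 4.2.11:

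> *If the episode that leads to stopping study drug itself meets the event definition, and its start date falls within a short pre-specified window after the last dose (for example 7 days), it is counted as an event at its start date and takes precedence over censoring.*

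Also:

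- State that a temporary interruption is not the intercurrent event, so that 4.2.1.3 agrees with the Table 9 footnote.
- Align the listed reasons with the new rule. Deleting pneumonia alone is not sufficient: SAE and the residual category remain, and 4.2.1.2 still censors at the last dose.
- State which date applies to a pneumonia event under the business rules, and whether the window overrides the end-of-treatment-visit cut-off in SAP 4.2.

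The time-at-risk formulas in 4.2.10 and 4.2.11 carry over. For an event k days after the last dose, the recovery term is 1 − k, so time at risk runs to the event's start date.

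Cost: SAP wording, settled by blinded staff before unblinding and recorded in SAP section 2 as a change to the protocol-planned analysis. Dosing dates, reasons for stopping and treatment dates are already collected. The downside is that a few events shortly after the last dose enter a while-on-treatment analysis. No change to the drug-stopping or restart rules is proposed.

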4.2.1.4 Primary Analysis of Primary Endpoint

Kaplan-Meier curves, region-stratified logrank test and region stratified Cox proportional hazard (PH) model results, will be provided for time to first COPDCompEx event as specified in Section 3.4.1.

The evidence of efficacy requires a two-sided region-stratified logrank test p-value ≤ 0.10 .

Kaplan-Meier curve estimates will be provided with a 90% CI.

Survival probabilities will be presented as survival curves estimated using the Kaplan-Meier method.

Diagnostic plot (log-log) will be presented to assess proportional hazard assumption.

The hazard ratio estimate from the Cox PH model will be provided with a 90% CI.

COPDCompEx data will be listed.

The analyses will be focused on the FAS population, including only those subjects with post-baseline eDiary data.

4.2.1.5 Sensitivity Analyses of the Primary Endpoint

Not applicable.

4.2.1.6 Supplementary Analyses of the Primary Endpoint

The analysis described above (Section 4.2.1.4) will be repeated applying the "treatment policy" estimand strategy as supportive. The events that occurred after intercurrent events will not be censored (i.e. will be treated as events). The treatment policy strategy used to estimate the efficacy of AZD4831 in 'real-world' conditions.

4.2.1.7 Subgroup Analyses

The subgroup analysis will be conducted for exploratory purposes.

The Cox proportional hazards model specified above would also be run separately with the "while on treatment" strategy for the following subgroups:

- Frequent Productive Cough (Yes; No)
- Gender (Male; Female)
- Age $(\ge 40 <65; \ge 65 \le 80)$
- Race (as collected in CRF)
- BMI (<18; ≥ 18 to <25; ≥ 25 to <30; ≥ 30)
- Geographic region (North America (Canada, United States of America), Eastern Europe (Bulgaria, Poland, Turkey), Western Europe (Denmark, Germany, Italy, Netherlands, Spain, United Kingdom), Rest of the world (Argentina, Mexico, South Africa).
- Baseline FEV1 as percent of predicted (<50%; ≥50%)
- Maintenance medications:
 - o ICS; no ICS
 - LABA/ICS; LABA/LAMA/ICS; LABA/LAMA
- Number of COPD exacerbations in last 24 months ($\langle 2; \geq 2 \rangle$)
- Type of site of recruitment (primary care site; specialist care site)
- Smoking status (Current smokers; Ex-smokers)
- MPO concentration at baseline (upper tertile; middle tertile; lower tertile)

The hazard ratio estimate from the Cox PH model will be provided with a 90% CI only for subgroup categories that contain at least 20% of the total participants.

